**Cycles 2 & 3**

4.3.2 Required Observations in Cycles 2 &3

- a. Hx/PE with VS including BP. Every 2 weeks. Please see [Section 5.5](#) for additional guidance regarding BP.
- b. Wt/Ht/Performance status. Day 1 of each Cycle.
- c. CBC/diff/platelets. Every 2 weeks.
- d. Electrolytes, BUN, creatinine, Ca++, PO4, Mg++, AST, ALT, albumin, bilirubin, urinalysis, amylase, lipase. Every 2 weeks. See [Section 5.4](#) for dose modifications due to proteinuria.
- e. TSH. Day 1 of each cycle. Patients found to have an abnormal TSH level should have a free T4 level measured. See [Section 5.10.2](#) for details and management of thyroid toxicity.
- f. ECG including QTc interval. End of Cycle 2.
- g. X-ray tibial growth plate. Prior to Cycle 2 in patients with open growth plates, follow-up plain radiographs of the same growth plate(s) should be obtained. See [Section 5.10.1](#) for details and management of growth plate toxicity.
- h. Patient diary. End of each cycle. For patient diary see [Appendix III](#).
- i. Pharmacodynamics. Prior to Cycles 2 and 3. See [Section 7.2.2](#) for details.
- j. Pregnancy test. Female patients of childbearing potential require a negative pregnancy test prior to the start of each cycle; sexually active patients must use an acceptable method of birth control.
- k. Tumor disease evaluation. End of Cycle 2. Tumor Disease Evaluation should be obtained on the next consecutive cycle after initial documentation of either a PR or CR. Please note that for solid tumor patients, if the institutional investigator determines that the patient has progressed based on clinical or laboratory evidence, he/she may opt not to confirm this finding radiographically.
- l. CEA, calcitonin (for patients with MTC only). End of Cycle 2. Calcitonin measurements should be obtained in the fasting state.

**This listing only includes evaluations necessary to answer the primary and secondary aims. OBTAIN OTHER STUDIES AS REQUIRED FOR GOOD CLINICAL CARE.**

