## 9.2 Study Design

### 9.2.1 Non-osteosarcoma Strata

The primary endpoint for the non-osteosarcoma strata will be objective response by RECIST criteria v 1.1. The best response of disease to XL184 (defined in [Section 10.4](#)) will be examined separately in each of the 3 primary disease groups. If 13 patients of the same histology enroll on either of the secondary strata (i.e., 13 Wilms tumor patients or 13 of the same type of eligible rare tumor patients), then the rule below will be applied to that group of patients. The following Simon’s minimax two-stage design will be used in all the non-osteosarcoma strata.

	Cumulative Number of Responses	Decision
Stage 1: Enter 13 patients	0	Terminate the trial early: agent ineffective
	1 or more	Inconclusive result, continue trial (proceed to Stage 2)
Stage 2: Enter 7 additional patients	2 or fewer	Terminate the trial: agent ineffective
	3 or more	Terminate the trial: agent effective

We will consider the agent not of sufficient interest for further evaluation in a disease category if the true response rate is 5% and of sufficient activity if the true response rate is 25%. If the agent has a true response rate of 5%, the rule described above will identify it of sufficient activity for further study with probability 0.074 (type I error),

and the trial will have an expected sample size of 16.4 with 51.3% probability of early termination. If the agent has a true response rate of 25%, the rule described above will identify it of sufficient activity for further study with probability 0.903 (power against the alternative hypothesis  $p = 0.25$ ). An expanded table of possibilities is below:

True response rate	Probability of stopping early for lack of activity	Probability of identifying agent as effective	Expected number of patients accrued
5%	0.513	0.074	16.41
10%	0.254	0.317	18.22
15%	0.121	0.586	19.15
20%	0.055	0.786	19.62
25%	0.024	0.903	19.83
30%	0.010	0.961	19.93
35%	0.004	0.986	19.97

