### 9.2.2 Osteosarcoma stratum-specific Design

For the osteosarcoma stratum, patients will be enrolled in two stages. In the first stage, 19 disease control and RECIST response evaluable patients will be enrolled. Each patient will be evaluated for both outcome measures: (1) disease control success; and (2) RECIST response (CR or PR v. not CR or PR). The decision rule for the two stage study design is summarized as:

	Cumulative response results	Decision
Stage 1: Enter 19 patients	$\leq 4$ disease control successes AND $\leq 1$ RECIST responders	Terminate the trial early: agent ineffective
	$\geq 5$ disease control successes OR $\geq 2$ RECIST responders	Inconclusive result, continue trial (proceed to Stage 2)
Stage 2: Enter 10 additional patients	$\leq 8$ disease control successes AND $\leq 4$ RECIST responders	Terminate the trial: agent ineffective
	$\geq 9$ disease control successes OR $\geq 5$ RECIST responders	Terminate the trial: agent effective

*Design Characteristics:* Each patient enrolled will be evaluated for: (1) complete or partial response as defined by the RECIST criteria where the first evaluation of CR or PR is made at or before the end of the sixth cycle of study therapy (denoted as R below); or (2) stable disease after four months of therapy or at the end of the sixth cycle, whichever occurs first (denoted as S below). We will not be interested in promoting the agent for further investigation if the probability of response in any particular individual is less than or equal to 0.05 ( $P(R) \leq 0.05$ ) and the probability of remaining analytic event free in any particular individual is less than or equal to 0.20 ( $P(S) \leq 0.20$ ). We will be interested in promoting the agent for further investigation if the probability of response in any particular individual is

at least 0.22 ( $P(R) \geq 0.22$ ) **or** the probability of remaining analytic event free in any particular individual is at least 0.42 ( $P(S) \geq 0.42$ ).

For the calculations below, it is assumed  $\Pr(S | R) = 0.90$ .

The statistical characteristics of this design are:

Probability of four month disease control	Probability of RECIST response	Probability of Stopping After Stage 1 (and concluding the drug is ineffective)	Probability of Concluding the Drug is Ineffective at the Conclusion of the Trial	Probability of Concluding the Drug is Effective at the Conclusion of the Trial
0.20	0.05	0.56	0.89	0.11
0.42	0.22	0.014	0.05	0.95
0.42	0.05	0.044	0.096	0.904

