#### 9.3.1 RECIST Response Criteria for all strata

Response criteria are described in [Section 10](#). A RECIST responder is defined as a patient who achieves a best response (as defined in [Section 10.6](#)) of PR or CR on the study. Response rates will be calculated as the percent of RECIST response-evaluable patients who are responders, and confidence intervals will be constructed accounting for the two-stage design.

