#### 9.4 Evaluability for Response

Any patient who is enrolled and receives at least one dose of XL184 will be considered evaluable for response and disease control provided: (1) the patient demonstrates progressive disease or death while on protocol therapy; or (2) the patient is observed on protocol therapy for at least one cycle and the tumor is not removed surgically prior to the time complete response or partial response is confirmed, or (3) the patient demonstrates a complete or partial response as confirmed according to protocol criteria. Patients who demonstrate a complete or partial response confirmed by central review will be considered to have experienced a response for the application of the rule given in [Section 10.2](#). The evaluation period for determination of the best response will be 6 treatment cycles. All other patients will be considered non-responders. All patients considered to have a response (CR or PR) must have imaging studies reviewed centrally at the COG. Centers will be notified by the COG about requests for scans of patients with stable disease. See [Section 7.3](#) regarding shipping instructions. Preliminary assessment of activity using institutionally provided tumor measurements will be entered into CDUS quarterly. The central review by COG will be provided as the final reviewed assessment of response when such becomes available.

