10.5.2 Overall Best Response Assessment

Each patient will be classified according to their “best response” for the purposes of analysis of treatment effect. Best response is determined from the sequence of the objective statuses described in [Section 10.6](#).

10.6 **Best Response (Solid Tumors)**

Two objective status determinations of disease status, by CT or MRI, obtained on two consecutive determinations, separated by at least a 3 week time period, are required to determine the patient’s overall best response. Two objective status determinations of CR before progression are required for best response of CR. Two determinations of PR or better before progression, but not qualifying for a CR, are required for a best response of PR. Two determinations of stable/no response or better before progression, but not qualifying as CR or PR, are required for a best response of stable/no response; if the first objective status is unknown, only one such determination is required. Patients with an objective status of progression on or before the second evaluations (the first evaluation is the first radiographic evaluation after treatment has been administered) will have a best response of progressive disease. Best response is unknown if the patient does not qualify for a best response of progressive disease and if all objective statuses after the first determination and before progression are unknown.

Table 1: Sequences of objective statuses with corresponding best response.

1 st Status	2 nd Status	3 rd Status	Best Response
Progression			Progressive disease
Stable, PR, CR	Progression		Progressive disease

Unknown	Progression		Progressive disease
Stable	Stable	Progression	Stable
Stable, Unknown	PR, CR	Progression	Stable
Stable, Unknown	Unknown	Progression	Unknown
PR	PR	Progression	PR
PR	CR	Progression	PR
PR, CR	Unknown	Progression	Unknown
CR	CR	Progression	CR
Unknown	Stable	Progression	Stable

Table 2: Overall Response for Patients with Neuroblastoma and Measurable Disease

CT/MRI	MIBG	Bone Scan	Bone Marrow	Catechol	Overall
PD	Any	Any	Any	Any	PD
Any	PD	Any	Any	Any	PD
Any	Any	PD	Any	Any	PD
Any	Any	Any	PD	Any	PD
SD	CR/PR/SD	Non-PD	Non-PD	Any	SD
PR	CR/PR	Non-PD	Non-PD	Any	PR
CR/PR	PR	Non-PD	Non-PD	Any	PR
CR	CR	Non-PD	Non-PD	Elevated	PR
CR	CR	CR	CR	Normal	CR

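### Does it matter that the plan does not say outright whether a PR first seen at the pre-Cycle 7 scan and confirmed afterwards counts as a response?

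*Combined protocol and SAP*

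**What the plan says.** Section 9.4 sets the window, "The evaluation period for determination of the best response will be 6 treatment cycles", and then the default, "All other patients will be considered non-responders". It names no stratum.

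Section 9.3.1, which covers all strata, defines a responder as a patient with a best response "of PR or CR on the study", and refers to Section 10.6 for the meaning of best response. Section 10.6 requires status determinations "obtained on two consecutive determinations, separated by at least a 3 week time period"; a best response of PR needs two determinations of PR or better before progression.

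The scans are set in Section 4.3.2 ("Tumor disease evaluation. End of Cycle 2") and Section 4.4.2 (before Cycles 5 and 7, then every third cycle). Both sections place the confirmatory scan on the next consecutive cycle after a PR or CR is first documented.

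For osteosarcoma only, Section 9.2.2 counts a response "where the first evaluation of CR or PR is made at or before the end of the sixth cycle of study therapy". Section 9.2.1, which covers the other strata, has no such sentence.

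Two cross-references are wrong. In Section 9.2.1, "The best response of disease to XL184 (defined in" leads to Section 10.4, the neuroblastoma MIBG criteria. In Section 9.4, "considered to have experienced a response for the application of the rule given in" leads to Section 10.2, which contains no decision rule; the rule is in Section 9.2.

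**The concern.** Three evaluations are tied to the six cycles. A PR first seen at the end of Cycle 2 or before Cycle 5 can be confirmed inside the window. One first seen before Cycle 7 cannot. Section 9.4 read literally drops that patient. The open-ended phrase in Section 9.3.1, or the first-documentation rule of Section 9.2.2 carried across, would keep the patient.

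The cut-offs are low: 0 against 1 response in 13 patients decides whether a stratum stops, and 2 against 3 in 20 decides whether the agent is called effective. One disputed patient could settle a stratum. The trial is open-label, so a definition settled after such a patient appeared could be influenced by the result.

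**Working it through.** **1. The plan's own figures.** Inputs from Section 9.2.1: 13 patients, stop at 0 responses; 7 more; effective at 3 or more of 20; rates 5% and 25%.

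P(effective) = Σ over x ≥ 1 of P(x of 13) × P(at least 3 − x of 7).

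- At 5%: 0.0736 (plan: 0.074).
- At 25%: 0.9030 (plan: 0.903).

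All seven rows of the Section 9.2.1 table reproduce. The calculation treats each patient as a responder or not at a given rate, so it holds for whichever single definition of response that rate refers to.

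**2. What the text gives when chained.** Section 9.3.1 defines a responder through Section 10.6. Section 10.6 makes a best response of PR depend on two determinations. Section 9.4 allows six cycles (6 × 28 = 168 days) for determining best response and makes everyone else a non-responder. With only one determination inside the window, the patient is not counted. Section 9.2.2 departs from this, but for one stratum with its own dual-endpoint design, where the specific rule can be followed.

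**3. Effect if a disputed patient exists.** Assume exactly one such patient, equally likely to be any of the 20, with the others undisputed responders at rate p. The final conclusions differ with probability

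(13/20) × [A + B] + (7/20) × C, where

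- A = P(0 of 12) × P(at least 2 of 7): the strict reading stops at stage 1 and the inclusive reading ends as effective;
- B = P(exactly 2 of 19, with at least 1 in the 12 other stage 1 patients);
- C = P(exactly 2 of 19, with at least 1 in the 13 stage 1 patients).

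At p = 0.05: 0.65 × (0.0240 + 0.1568) + 0.35 × 0.1631 = 0.1746. At p = 0.25: 0.65 × (0.0176 + 0.0705) + 0.35 × 0.0733 = 0.0829.

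If the disputed patient is among the first 13, the stage 1 decision differs when none of the other 12 responds, with probability (1 − p)^12.

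| p | Final conclusions differ | Stage 1 differs (patient in first 13) |
|---|---|---|
| 0.05 | 0.175 | 0.540 |
| 0.10 | 0.281 | 0.282 |
| 0.15 | 0.242 | 0.142 |
| 0.20 | 0.156 | 0.069 |
| 0.25 | 0.083 | 0.032 |

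**4. Effect without assuming that the patient exists.** Let f be the share of responses first seen at the pre-Cycle 7 scan. The documents give no value; 10% and 20% are assumptions. The strict reading then counts responses at rate p(1 − f). Every strict responder is also an inclusive one, so the readings disagree with probability equal to the difference between the two chances of declaring the agent effective.

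| True rate | f | Inclusive | Strict | Disagree |
|---|---|---|---|---|
| 5% | 10% | 0.0736 | 0.0571 | 0.0165 |
| 5% | 20% | 0.0736 | 0.0427 | 0.0309 |
| 25% | 10% | 0.9030 | 0.8535 | about 0.05 |
| 25% | 20% | 0.9030 | 0.7858 | about 0.117 |

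If 5% and 25% are already rates of response confirmed within six cycles, the strict rule has exactly the stated operating characteristics.

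**The case for a change.** The best case for an amendment is that the plan uses two anchors for one endpoint. Section 9.4 has no stratum limit, so it conflicts with Section 9.2.2 even within osteosarcoma, and the silence of Section 9.2.1 could mean the same intent or a deliberate difference. The same doubt reaches any Wilms or rare-tumor histology that enrolls 13 patients, because the two-stage rule then applies to it. One sentence would remove the doubt, no scan would be added, and it is better written before a disputed case is seen.

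The tension is real and that part stands. It does not show that the plan as written misleads. Either rule would serve, and the literal text already supplies one. The inclusive rule is a choice with its own costs: it counts more patients than Section 9.4 literally allows, in an open-label trial with accrual under way, and it delays some response calls by a cycle. If the 5% null refers to responses confirmed within six cycles, counting late confirmations raises the type I error from 0.074 to 0.094 when f is 10%, or 0.123 when f is 20%. The edge is also not as sharp as it looks: the therapy delivery map charts the pre-cycle scan on Day 1, and Section 4.0 tolerates departures of up to 72 hours.

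The wrong references to Sections 10.4 and 10.2 are clerical. Section 9.3.1 and Section 10.3.4 both cite Section 10.6 correctly, and the Simon rule appears only in Section 9.2.1.

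**Conclusion.** No change to the plan follows. An analyst who applies Sections 9.3.1, 10.6 and 9.4 together reaches a definite answer for the non-osteosarcoma strata: a PR not confirmed within six cycles is not a response. For osteosarcoma the stratum's own first-documentation rule applies. The design figures of 0.074 and 0.903 are correct.

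The probabilities of 8% to 28% are conditional on one disputed patient being present. Such a patient must pass the first two scans without PR or progression, first respond at the third, and then confirm. Under the assumed shares of 10% and 20%, the readings disagree in about 2% to 3% of strata at the 5% rate and about 5% to 12% at the 25% rate. Those shares are illustrative, since the documents say nothing on response timing. Relative to the inclusive reading, the literal one errs toward caution: it lowers the chance of a false positive and gives up some power only if the design rates were meant to include late-confirmed responses.

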#### 9.5 Evaluability for Toxicity

All patients who receive at least one dose of XL184 according to protocol guidelines will be considered in the evaluation of toxicity.

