### 9.3 Methods of Analysis

Toxicity tables will be constructed to summarize the observed incidence by type of toxicity and grade. A patient will be counted only once for a given toxicity for the worst grade of that toxicity reported for that patient. Toxicity information recorded will include the type, severity, time of onset, time of resolution, and the probable association with the study regimen.

Time-to-event analyses (time to progression, progression-free survival, and overall survival) will be computed when all patients in a stratum have at least one year of follow-up.

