9.3.4 Adverse Event Monitoring Rule

We will use a Bayesian rule to monitor for protocol-specific toxicities. We will assume a beta prior distribution with  $\alpha = 0.52$  and  $\beta = 2.08$ . At least once per month, we will calculate the posterior probability (given the data) that the probability of protocol-specific toxicity exceeds the 20% threshold:

$$P(p_{\text{protocol-specific toxicities}} > 20\% | \text{Data}) = \int_{0.2}^1 \frac{\binom{n}{x} p^x (1-p)^{n-x} \frac{\Gamma(2.6)}{\Gamma(0.52)\Gamma(2.08)} p^{-0.48} (1-p)^{1.08}}{\int_0^1 \binom{n}{x} q^x (1-q)^{n-x} \frac{\Gamma(2.6)}{\Gamma(0.52)\Gamma(2.08)} q^{-0.48} (1-q)^{1.08} dq} dp$$

Here  $n$  is the number of protocol-specific toxicity-evaluable cycles and  $x$  is the number of such cycles on which a protocol-specific toxicity event is observed. Examples of situations in which this rule will indicate protocol-specific toxicities have been noted and are presented below:

Number of failures	Number of patient-cycles
2	6
3	10
4	14
5	19
6	23
7	28
8	32
9	37
10	41
11	46
12	51

13	55
14	60

Protocol-specific toxicities of interest include fatigue, headache, proteinuria, hypertension, reversible posterior leukoencephalopathy syndrome (RPLS), palmar-plantar erythrodysesthesia, oral mucositis, ALT increase, lipase increase, bilirubin increase, diarrhea, thrombocytopenia, hypothyroidism, nausea, anorexia, neutropenia, weight loss and vomiting.

If there is strong evidence (posterior probability of at least 70% with at least 2 observed toxicities) that there is a per course protocol-specific toxicity probability of more than 20%, such information will be presented to the DSMC.

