**APPENDIX IV: XL184 DOSING NOMOGRAM**

**If a patient's dose is reduced due to toxicity, any future XL184 total weekly dose should not exceed a previously un-tolerated dose.**

See [Section 5.11](#) for the XL184 dose reduction table.

XL184 (Cabozantinib)	
40 mg/m^2/day	
BSA (m^2)	Weekly Dose/ Schedule for Initial Dosing
0.35 – 0.39	100 mg = 20 mg M, W, Th, Sat, Sun (or Day 1, 3, 4, 6, 7 of each week)
0.40 – 0.45	120 mg = 20 mg M, T, W, F, Sat, Sun (or Day 1, 2, 3, 5, 6, 7 of each week)
0.46 – 0.55	140 mg = 20 mg Daily
0.56 – 0.64	160 mg = 40 mg M, W, F, Sun (or Day 1, 3, 5, 7 of each week)
0.65 – 0.78	200 mg = 40 mg M, W, Th, Sat, Sun (or Day 1, 3, 4, 6, 7 of each week)
0.79 – 0.90	240 mg = 40 mg M, T, W, F, Sat, Sun (or Day 1, 2, 3, 5, 6, 7 of each week)
0.91 – 1.09	280 mg = 40 mg Daily
1.10 – 1.17	300 mg = 60 mg M, W, Th, Sat, Sun (or Day 1, 3, 4, 6, 7 of each week)
1.18 – 1.36	360 mg = 60 mg M, T, W, F, Sat, Sun (or Day 1, 2, 3, 5, 6, 7 of each week)
1.37 – 1.65	420 mg = 60 mg Daily
1.66 – 1.85	480 mg = 80 mg M, T, W, F, Sat, Sun (or Day 1, 2, 3, 5, 6, 7 of each week)
1.86 – 2.07	560 mg = 80 mg Daily
≥ 2.08	600 mg = 100 mg M, T, W, F, Sat, Sun (or Day 1, 2, 3, 5, 6, 7 of each week)

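### Section 9.5 makes toxicity evaluability depend on a protocol-compliant dose; the set should be every enrolled patient who received any XL184

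*Combined protocol and SAP*

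**What the plan says.** Section 9.5 defines the toxicity population in one sentence: "All patients who receive at least one dose of XL184 according to protocol guidelines will be considered in the evaluation of toxicity". It does not explain what a dose has to satisfy to meet the condition, and no other section says how treated patients outside this set are analysed.

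Section 9.4 defines the response population: "Any patient who is enrolled and receives at least one dose of XL184 will be considered evaluable for response and disease control provided" one of three conditions is met. These are progression or death on protocol therapy, at least one cycle of observation with the tumor not surgically removed before response is confirmed, or a confirmed response. None concerns whether the dose was compliant.

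Section 9.3 says "Toxicity tables will be constructed to summarize the observed incidence by type of toxicity and grade" and names no population. In 9.3.4, *n* "is the number of protocol-specific toxicity-evaluable cycles". That term is not defined and 9.5 is not cited. The DSMC is informed when the posterior probability of a "per course protocol-specific toxicity probability of more than 20" percent reaches 70%, with at least two toxicities observed.

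**The concern.** Defining toxicity is a stated secondary aim (1.2.1). The usual safety population is everyone exposed to the drug, because a patient dosed outside the rules is still exposed. Here the condition sits on the safety set and not on the response set, so one patient could count for response and not for toxicity.

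The condition may also be informative. One compliant dose is enough to qualify, so a patient whose dosing error is corrected enters the set. A patient who stops before correction, possibly because of toxicity, does not.

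Two things are at stake: whether the toxicity rates have a complete numerator and denominator, and whether the monthly monitoring rule counts every treated cycle.

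**Working it through.** **1. Dosing conditions side by side.**

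- Toxicity (9.5): one dose, with an undefined compliance condition.
- Response (9.4): one dose, no compliance condition, other provisos.
- Disease control (9.3.2, loss-to-follow-up example): one dose, no compliance condition.
- Pharmacokinetics (9.6): the full dose on Cycle 1 Day 1, an explicit dosing condition.

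So 9.6 states its dosing requirement in checkable terms, and 9.5 does not.

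**2. Who would be left out.** Appendix IV has 13 BSA bands, and every schedule includes Day 1. The amount per dosing day is 20 mg in 3 bands, 40 mg in 4, 60 mg in 3, 80 mg in 2 and 100 mg in 1. Of the 12 steps to the next band up, only four change that amount:

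- 140 to 160 mg/week: 160/140 = +14%
- 280 to 300 mg/week: 300/280 = +7%
- 420 to 480 mg/week: 480/420 = +14%
- 560 to 600 mg/week: 600/560 = +7%

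In the other 8 the Day 1 dose is the same in both bands. The largest step, 160 to 200 mg (+25%), is among these 8. The upper band reads "200 mg = 40 mg M, W, Th, Sat, Sun (or Day 1, 3, 4, 6, 7 of each week"; the lower band also gives 40 mg on Day 1. If compliance is judged dose by dose, most one-band errors therefore leave the patient evaluable. Only a patient with no compliant dose at all is left out.

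**3. The plan's own alert table.** Inputs from 9.3.4: a beta prior with α = 0.52 and β = 2.08 (mean 0.52/2.60 = 0.20), threshold 0.20, trigger 0.70. After *x* event cycles among *n*, the posterior is Beta(0.52 + *x*, 2.08 + *n* − *x*), and the rule uses P(p > 0.20). For each *x*, the largest *n* with a posterior of at least 0.70 was found. All 13 tabulated pairs are reproduced.

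**4. Effect of leaving out one cycle.** The documents give no misdosing rate, so one or two excluded cycles are assumed. Dropping an event cycle turns *x*/*n* into (*x* − 1)/(*n* − 1).

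| Boundary *x*/*n* | Posterior | One further event-free cycle, *x*/(*n* + 1) | One event cycle dropped |
|---|---|---|---|
| 2/6 | 0.7001 | 0.6318 | 0.4267 |
| 3/10 | 0.7147 | 0.6604 | 0.5022 |
| 4/14 | 0.7297 | 0.6840 | 0.5528 |
| 5/19 | 0.7042 | 0.6636 | 0.5455 |
| 6/23 | 0.7220 | 0.6857 | 0.5812 |
| 7/28 | 0.7051 | 0.6715 | 0.5739 |
| 8/32 | 0.7223 | 0.6915 | 0.6028 |
| 9/37 | 0.7095 | 0.6803 | 0.5960 |
| 10/41 | 0.7257 | 0.6986 | 0.6206 |
| 11/46 | 0.7152 | 0.6893 | 0.6142 |
| 12/51 | 0.7061 | 0.6812 | 0.6088 |
| 13/55 | 0.7215 | 0.6980 | 0.6300 |
| 14/60 | 0.7135 | 0.6908 | 0.6248 |

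Dropping one event cycle cancels the alert in every row (0.43-0.63 against 0.70). Dropping two gives 0.11-0.53. The third column shows the opposite effect. One cycle past each boundary there is no alert, and dropping one event-free cycle restores it (2/7 = 0.632 becomes 2/6 = 0.700).

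**5. Effect on a crude rate.** At the planned total of 146 (Section 9.7), leaving out one patient with an event changes the rate from (*x* + 1)/146 to *x*/145. The difference is (145 − *x*)/(146 × 145), at most 1/146 = 0.7 percentage points.

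**The case against.** A reader might infer that patients misdosed from Day 1, as those at highest risk, drop out of the safety tables and the DSMC alert, that their events vanish, and that toxicity is always understated. The documents do not support this.

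- One compliant dose is enough, and the dose is recalculated from BSA before each cycle (4.2.3, 4.3.3, 4.4.3). A bad start alone does not exclude a patient.
- Misdosing can be underdosing. No rate, direction or risk is given, and the table above shows that exclusion can create an alert as well as cancel one.
- Events are not lost. Expedited reporting (11.2, 11.8), routine reporting of Grade 3 and higher events (11.10) and the duty to bring unexpected frequencies of serious events to the DSMC (12.2) carry no compliance condition.
- Exclusion from the monitoring rule is inferred, because 9.3.4 neither defines its term nor cites 9.5.
- Because of 9.4's provisos, the response and toxicity denominators would differ even without the qualifier. The difference alone does not show a defect.
- The qualifier may only mean XL184 taken on study. Section 3.1.5, for instance, makes patients who start before enrollment ineligible.

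All of this stands, and it limits the point to a narrow one. It does not remove it. If the qualifier means only on-study treatment, it should say so. Individual event reports do not supply the complete numerator and denominator that rates and the monitoring rule need. 9.5 is also the only definition of toxicity evaluability that a reader of 9.3.4 can turn to.

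**Conclusion.** The point holds in narrow form. On a literal reading, 9.5 leaves treated patients with no compliant dose out of the toxicity evaluation, and the test for compliance is undefined. Their removal from the 9.3.4 rule is a natural inference, not a stated rule.

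The group is probably very small, and its size cannot be estimated from the documents. The effect on a crude rate is at most 0.7 percentage points per excluded patient at full accrual. The effect on monitoring matters only near a boundary, where one cycle decides the alert in either direction. That result assumes that 9.5 governs which cycles count and that one or two cycles are excluded. An alert leads to a presentation to the DSMC, not to an automatic stop.

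**What to change.** In 9.5, delete the four words that follow the drug name, so that every enrolled patient who receives any XL184 is evaluable for toxicity. In 9.3.4, define a toxicity-evaluable cycle to match, for example any cycle in which such a patient took at least one dose. Name the same population for the toxicity tables in 9.3. Flag dosing deviations in a listing and, if wanted, add a sensitivity table without those patients.

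The cost is a few words of text. Sample size, alert boundaries and clinical rules do not change. This is a free improvement.
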